11.4 ELECTROCARDIOGRAM

Descriptive statistics (n, mean, SD, median, minimum and maximum) for ECG parameters (heart rate, RR interval, PR interval, QRS duration, QT interval, and QTc) and changes from baseline values at each assessment time point to the end of study will be presented for the OLTP, and by treatment group for the DBTP. The QTc will be calculated using both the Bazett and Fridericia corrections.

ECG parameter values are considered PCS if they meet or exceed the higher-limit PCS criteria listed in [Table 11-5](#). The number and percentage of patients with PCS postbaseline ECG values will be tabulated for the OLTP, and by treatment group for the DBTP. The percentages will be calculated relative to the number of patients with available non-PCS baseline values and at least 1 postbaseline assessment for the corresponding periods (OLTP or DBTP). The numerator is the total number of patients with available non-PCS baseline values and at least 1 PCS postbaseline value for the corresponding periods (OLTP or DBTP). A supportive tabular display of patients with PCS postbaseline values will be provided, including the PID number, baseline, all postbaseline (including non-PCS) values, and change from baseline.

In addition, a tabular display showing all AEs that occurred in patients who had postbaseline PCS ECG values will be provided.

A shift table from baseline to the end of study in the Investigator's overall interpretation of the ECG will be presented for the OLTP, and by treatment group for the DBTP for the following categories: normal; abnormal, not clinically significant; abnormal, clinically significant. A listing of patients with postbaseline clinically significant ECG abnormalities according to the Investigator's or by the central cardiologist's overall interpretation will be provided.

The number and percentage of patients with an increase > 30 msec but ≤ 60 msec, and with an increase > 60 msec in QTcB or QTcF will be tabulated. Patients will be counted only once for the most severe category. A supportive listing of patients with postbaseline QTcB or QTcF increases > 30 msec will be provided, including the PID number, study center, and all QTc values (including changes from baseline). A listing of all AEs for patients with postbaseline QTcB or QTcF increases > 30 msec will also be provided.

Table 11-5 Criteria for Potentially Clinically Significant Electrocardiograms

Parameter	Unit	Higher Limit
QRS duration	msec	≥ 150
PR interval	msec	≥ 250
QTcB	msec	> 500
QTcF	msec	> 500

QTcB = QT interval corrected for heart rate using the Bazett formula $QT/ (RR)^{1/2}$; QTcF = QT interval corrected for heart rate using the Fridericia formula ($QTcF = QT/ (RR)^{2/5}$).

11.5 OTHER SAFETY PARAMETERS

Other safety parameters include ophthalmologic parameters, C-SSRS, and EPS scales (AIMS, BARS, and SAS).

11.6 OPHTHALMOLOGIC PARAMETERS

Ophthalmological parameters include best corrected visual acuity (BCVA); intraocular pressure (IOP); lens status and lens opacity; color discrimination; and slit-lamp biomicroscopy examination results.

Descriptive statistics (n, mean, SD, minimum, median, and maximum) for each numeric ophthalmologic parameter and changes from baseline at each assessment time point will be presented overall for the OLTP and by treatment group for the DBTP.

The number and percentage of patients with a change from baseline in visual acuity $\geq +0.3$ in each eye and in either eye will be summarized overall for the OLTP, and by treatment group for the DBTP.

The number and percentage of patients with postbaseline IOP > 21 mm Hg will be presented. A supportive listing will be provided, including PID number, baseline and postbaseline IOP values.

The number of patients with phakic, pseudophakic, and aphakic lens status will be presented overall for the OLTP in the OL Safety population and by treatment group for the DBTP in the DB Safety Population. For patients with phakic eyes, the number and percentage of patients with cataract will be assessed by presence and severity of nuclear, cortical, and posterior subcapsular cataract lens opacities using a 3-point scale (0: absent, 1: $<$ standard photo #2, and 2: \geq standard photo #2). Patients with nuclear, cortical, or posterior subcapsular cataract lens opacities will be summarized for each eye (left and right) and for either eye using the higher scale of the 2 eyes overall in the OL Safety Population for the OLTP, for the SFU period in patients with opacity assessment, by treatment group for the DBTP in the DB Safety Population, and by treatment group during the SFU period in patients with opacity assessment in the DB safety population. A patient will be counted once in the highest lens opacity severity in the specific period. A

supportive listing will be provided, including PID number, baseline and postbaseline assessment values.

In addition, a shift table from normal baseline to abnormal postbaseline in color discrimination, slit-lamp biomicroscopy examination results will be provided overall for the OLTP and by treatment group for the DBTP.

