10. Patient requires concomitant treatment with any prohibited medication, supplement, or herbal product including any psychotropic drug or any drug with psychotropic activity or with a potentially psychotropic component (for exceptions allowed for concomitant treatments, refer to [Section 4.8](#)).
11. At Visit 2, patient requires pharmacologic treatment for the control of EPS.
12. Prior participation in any clinical trials involving experimental or investigational drugs within 6 months before Visit 1 or planned during the study.

Other Medical Criteria:

13. Female patients who are pregnant, planning to become pregnant during the course of the study, or are currently lactating.

14. Any concurrent medical condition including psychiatric symptoms possibly secondary to any other general medical condition (eg, Vitamin B-12/folate deficiency, Cushing syndrome, etc) that, in the judgment of the investigator, might interfere with the conduct of the study, confound the interpretation of the study results, or endanger the patient's well-being.
15. Any cardiovascular disease (eg, hypertension) or endocrinological disease (eg, thyroid disease/disorders) that is clinically unstable, or decompensated, based on the investigator's judgment.
16. Gastric bypass or any condition that would be expected to affect drug absorption (lap band procedures and gastric sleeve are acceptable if there is no problem with absorption).
17. History of seizure disorder (with the exception of febrile seizure), stroke, significant head injury, tumor of the central nervous system, or any other condition that predisposes toward a risk of seizure.
18. Patients who meet any of the following ophthalmological criteria:
 - a. A clinically significant finding of lens opacification(s) at the screening ophthalmological examination that meets any of the following:
 1. Opacification \geq AREDS standard photo #2
OR
 2. Best-corrected visual acuity worse than LogMar 0.1 [20/25 Snellen equivalent]
OR
 3. Cataract surgery is planned or expected at anytime during the trial, based upon the ophthalmological examination.
 - b. Any clinically significant ocular trauma or complications of ocular trauma, or history of retinal detachment, intraocular surgery (with the exception of cataract surgery to remove or replace lenses bilaterally) or laser treatment
 - c. History or current findings of ocular disease (eg, open- or narrow-angle glaucoma, retinopathies, corneal diseases)

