6.5.2 Ocular Adverse Events of Special Interest

The sponsor is required to perform expedited reporting to worldwide regulatory authorities of ocular AESIs that meet specific criteria. Therefore, the sponsor must be notified immediately regarding any ocular AESIs that occur after informed consent is obtained.

The following serious and non-serious ocular AESIs require immediate notification:

- Cataract*, lens or lenticular abnormality or change, opacity, opacification or opalescence
- Blindness, night blindness, visual acuity or vision decrease, abnormality or change, visual acuity test abnormality or change
- Retinal, macular, or optic nerve degeneration, abnormality or change; retinal pigment epithelium detachment, abnormality or change
- Color vision decrease, abnormality or change

Within 24 hours of learning of any serious or non-serious AESIs, the study site personnel must report the event on the SAE/AESI form for clinical trials.

*NOTE: When determining whether to report an event as a cataract, please take into consideration the AREDS scoring of that lens opacity. Only those changes that have reached the threshold of *equal to or greater than AREDS standard photo #2* should be reported as a cataract.

In addition to completing the appropriate form, the medical monitor may also be notified by telephone.

All ocular AESIs are to be followed by the study staff until resolution or until the ocular AESI is deemed stable. The sponsor may contact the study site to solicit additional information or follow-up on the event.

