7.3.4.5.3 Ophthalmological Parameters

Ophthalmological parameters include best-corrected visual acuity (BCVA); intraocular pressure (IOP); lens opacity; color discrimination; and slit-lamp biomicroscopy examination results.

Descriptive statistics for each numeric ophthalmological parameter (eg, visual acuity, IOP) and changes from Baseline at each assessment timepoint will be presented.

The number and percentage of patients with a change from Baseline in visual acuity $\geq +0.3$ in each eye and in either eye will be summarized overall for the OL treatment period, and by treatment group for the DB treatment period.

The number and percentage of patients with postbaseline IOP > 21 mm Hg will be presented. A supportive listing will be provided, including PID number, Baseline and postbaseline IOP values.

The number of patients with phakic, pseudophakic, and aphakic lens status will be summarized for both the OL and DB treatment periods. For patients with phakic eyes, the number and percentage of patients with cataract will be assessed by presence and severity of nuclear, cortical, and posterior subcapsular cataract lens opacities using a 3-point scale (0: absent, 1: < standard photo #2, and 2: \geq standard photo #2). Patients with nuclear, cortical, or posterior subcapsular cataract lens opacities will be summarized for each eye (left and right) and for either eye using the higher scale of the 2 eyes by treatment group for each period (OL, DB, and SFU periods). A patient will be counted once in the highest lens opacity

severity in the specific period. A supportive listing will be provided, including PID number, Baseline and postbaseline assessment values.

In addition, a shift table from normal Baseline to abnormal postbaseline in color discrimination, slit-lamp biomicroscopy examination results will be provided.

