12.16 Protocol Amendment #4 Summary

Title: A Double-blind, Placebo-controlled, Randomized Withdrawal, Multicenter Clinical Trial Evaluating the Efficacy, Safety, and Tolerability of Cariprazine in a Dose-Reduction Paradigm in the Prevention of Relapse in Patients With Schizophrenia

Study RGH-MD-24 Amendment 4

Date of Amendment 4: 17 December 2019

Amendment Summary

This summary includes changes made to Protocol RGH-MD-24 Amendment 3 (28 November 2018).

Minor editorial and document formatting revisions have not been summarized. The following is a summary of the major changes that were made to each section of the protocol, and a brief rationale for these changes.

Section	Major Revision	Rationale
Global	Phrase ocular events of special interest changed to ocular AESIs.	For clarity.
Global	There is no longer a distinct SAE reporting form and AESI reporting form. It is a combined SAE/AESI form.	To reflect an administrative change in forms.
4.4 Exclusion Criteria	Exclusion Criterion #18a revised.	In light of ophthalmology consultation and FDA feedback, criterion revised to allow for inclusion of patients with non-clinically significant opacifications in order to facilitate recruitment.
6.5.2 Ocular Adverse Events of Special Interest	Addition of a text note with associated asterisk to clarify reporting requirements specifically around cataracts.	Text amended to provide direction regarding cataract reporting when using the AREDS grading system, consistent with regulatory feedback.
9.1.2 Serious Adverse Event	Text revised to clarify which pregnancy outcomes or genetic abnormalities are considered SAEs.	For clarity.
12.10 Ophthalmological Examination	Protocol was updated to specify that color vision testing is to be completed using HRR color plates for newly screened patients.	To standardize data collection.

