6.7 DOUBLE-BLIND INTENT-TO-TREAT POPULATION

The DB ITT population will consist of all patients who took at least 1 dose of DB IP and had at least 1 post-randomization assessment of the PANSS or CGI-S scores during the DBTP of the study.

Patients will be included in the randomized treatment group for the DB ITT population.

7.0**STUDY PATIENTS****7.1****PATIENT DISPOSITION**

The OLTP starts with the first dose of OLTP and ends with one of the following: the last scheduled assessment at the Visit 13/end of OLTP (Week 18) or early termination (ET) before Visit 13 (Week 18) for patients who do not enter the DBTP; or 1 day before the first dose of DBTP (or the date of the first dose of the DB IP if the last scheduled assessment date in the OLTP is on the date of the first dose of the DBTP) for patients who enter the DBTP.

The DBTP starts with the first day of randomization and ends with the last scheduled assessment at Visit 26 (Week 44) or ET.

The SFU period starts one day after the end of the previous period and ends with the last available assessment. For patients without Visit 27 (Week 46) or Visit 28 (Week 48) assessment, the SFU period would not be derived.

Screen-failure patients (ie, patients screened but not included in the OL Safety Population) and the associated reasons for failure will be tabulated overall for the Screened Population.

The number and percentage of patients in the Screened, OL Safety and OL ITT Populations will be summarized overall and by study center. The number and percentage of patients in the Randomized, DB Safety, and DB ITT Populations will be summarized overall by treatment group and by treatment group and study center.

The number and percentage of patients in the OL Safety Population, who prematurely discontinued from the OLTP, who completed the OLTP, who entered the DBTP, and who entered the SFU period will be summarized overall and by reasons for premature discontinuation as recorded on the respective disposition pages of the electronic case report form (eCRF).

Similarly, the number and percentage of patients in the DB Safety Population who completed the DBTP, who prematurely discontinued from the DBTP, and who entered the SFU period will be summarized overall, by DB treatment group and by reasons for premature discontinuation as recorded on the respective disposition pages of the eCRF. Patients who relapse during the DBTP will also be summarized as completing the study.

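### The lens-opacity table counts each patient's highest grade per period without reference to screening, so opacity already present at entry is tabulated as an on-treatment finding

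*SAP*

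**What the plan says.** Entry. Criterion 18a in Protocol 4.4 excludes "A clinically significant finding of lens opacification(s) at the screening ophthalmological examination that meets any of the following": opacity at or above AREDS photo #2, best-corrected acuity worse than logMAR 0.1, or cataract surgery planned or expected. Opacity below photo #2 with adequate acuity is not excluded. The Amendment 4 summary (Protocol 12.16) shows that this is deliberate: "criterion revised to allow for inclusion of patients with non-clinically significant opacifications in order to facilitate recruitment".

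The table. In phakic eyes, SAP 11.6 states that "the number and percentage of patients with cataract will be assessed by presence and severity of nuclear, cortical, and posterior subcapsular cataract lens opacities", on a scale of 0 (absent), 1 (below photo #2) and 2 (photo #2 or worse). The counting rule is "A patient will be counted once in the highest lens opacity severity in the specific period". Protocol 7.3.4.5.3 has the same rule ("A patient will be counted once in the highest lens opacity"). Results are given overall for the open-label period and by treatment group for the double-blind period. Baseline grade appears only in a supportive patient listing.

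Other lens-related output. SAP 11.6 plans "a shift table from normal baseline to abnormal postbaseline in color discrimination, slit-lamp biomicroscopy examination results will be provided"; lens opacity is not named there. Ocular events of special interest, which include lens opacity and lens change, are summarised separately as treatment-emergent events (Protocol 6.5.2 and 7.3.4.1; SAP 11.1).

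Reporting scope. The study was terminated early. SAP Appendix IV limits the abbreviated report to a listed subset of analyses. That subset includes ocular-event summaries and a listing of the eye examination and lens status, but not the lens-opacity summary table.

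**The concern.** Both study objectives include safety, and lens change is a named event of special interest. A summary of lens findings by period should let the reader see what appeared or worsened on treatment. A count of the worst grade in a period does so only if everyone starts at grade 0, and the eligibility criteria allow otherwise.

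The same SAP refers to baseline in comparable places. Potentially clinically significant laboratory and ECG values require a baseline that was not already significant (11.2, 11.4). Treatment-emergent parkinsonism and akathisia require a baseline score at or below the cut-off (11.7.1). Visual acuity, in the same section as lens opacity, is analysed as change from baseline. The lens table is out of line with that practice.

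The wording adds to the problem. The table speaks of patients with cataract while its scale includes grade 1. For event reporting, Protocol 6.5.2 reserves that word: "Only those changes that have reached the threshold of" photo #2 or worse are to be called cataract. A grade 1 count under a cataract label could be misread as an on-drug cataract rate, especially in the open-label period, which has no comparator.

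**Working it through.** No stated figure depends on this point, so there is none to reproduce. The check sets the definitions side by side and then illustrates the size.

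**Step 1: where the screening examination falls.** Eye examinations are at Visits 1, 13 and 26/ET, and at Visit 28 after a postbaseline cataract finding (Protocol 6.5.7). On the open-label period, SAP 7.1 says: "The OLTP starts with the first dose of OLTP and ends with one of the following". The Visit 1 examination must precede the first dose, so it belongs to no tabulated period. The footnote to SAP Table 16-1 maps Visit 13 eye examinations to the open-label period.

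**Step 2: what stops a lens finding from carrying forward.** Nothing does. The randomization criteria (Protocol 4.6) contain no lens condition, and the withdrawal criteria (8.9) do not list a lens finding.

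**Step 3: apply the rule to four patterns in one eye.**

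| Visit 1 / 13 / 26 grade | Open-label count | Double-blind count | What happened |
|---|---|---|---|
| 1 / 1 / 1 | grade 1 | grade 1 | no change |
| 0 / 0 / 1 | grade 0 | grade 1 | new in double-blind |
| 0 / 2 / 2 | grade 2 | grade 2 | arose in open-label only |
| 1 / 1 / 2 | grade 1 | grade 2 | progressed in double-blind |

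In the double-blind table the first two rows look identical, and so do the last two. In the third row the patient may be on placebo, and a lens change that arose on open-label cariprazine is then shown under placebo.

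**Step 4: does the shift table cover the lens?** The structures listed for slit-lamp examination in Protocol 6.5.7 omit the lens, although the next paragraph says that biomicroscopic findings are evaluated for lens opacities. SAP 11.6 lists lens status and opacity separately from slit-lamp results. Coverage is therefore not stated. Even if the lens were included, a shift from normal to abnormal would not show grade 1 moving to grade 2.

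**Step 5: size.** Let n = 115 per arm (planned; SAP 4.0), p = prevalence of grade 1 at screening, and i = incidence of new opacity among patients without it. The documents give neither p nor i, so both are assumed.

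- Count under the rule = n·p + n·(1 − p)·i
- Newly emergent count = n·(1 − p)·i

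| p | Count if i = 0 | Count if i = 2% | Emergent if i = 2% | Share pre-existing if i = 2% |
|---|---|---|---|---|
| 5% | 5.8 | 7.9 | 2.2 of 109 | 72% |
| 10% | 11.5 | 13.6 | 2.1 of 104 | 85% |
| 20% | 23.0 | 24.8 | 1.8 of 92 | 93% |
| 30% | 34.5 | 36.1 | 1.6 of 81 | 96% |

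**Step 6: dilution.** Take p = 20% in two arms, with i = 0 in one and 2% in the other. The table shows 23.0/115 = 20.0% against 24.8/115 = 21.6%, a ratio of 24.8/23.0 = 1.08. Restricted to patients clear at screening, the contrast is 0 against 1.8 of 92 (2%).

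**The case against.** Several counter-arguments have force.

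- A reader might infer that the table hides true progression to grade 2. It does not. Grade 2 is excluded at screening, so apart from eligibility deviations every grade 2 count is a worsening since entry, and the severity split keeps it visible. What the table does not show is whether it came from grade 0 or grade 1 and, in the double-blind table, whether it arose before or after randomization. The patient listing can answer both.
- A reader might infer that emergent lens change goes unreported. That is also wrong. The events of special interest in Protocol 6.5.2 include opacity and lens change as well as cataract, and only events that begin or worsen after the first open-label dose count as treatment-emergent. A stable screening opacity does not inflate that summary.
- A reader might infer bias against cariprazine or against placebo. Randomization at 1:1:1 should spread opacity present by Visit 13 about evenly across the arms, so no direction is implied.
- A reader might see a contradiction with Protocol 6.5.2. That section governs event reporting, while SAP 11.6 tabulates graded findings with each grade defined. Only the loose cataract label stands as a fault.
- The table is not scheduled for the abbreviated report, so the fault may never reach a reader.
- The prevalence range is assumed and is applied to planned arm sizes in a study that stopped early. One prevalence for all patients is also doubtful, because criterion 18a was relaxed only in December 2019.

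These points limit the consequences. None of them supplies the missing reference to screening grade.

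**Conclusion.** The point holds as a limited fault in the summary table. Grade 1 opacity is admitted at entry and then counted, unchanged, in the open-label period and again in the double-blind arm. Grade 2 opacity that arose open-label is likewise recounted under the arm that follows. The table therefore reports prevalence in each period. Absolute rates are inflated and differences between arms diluted, with no directional bias.

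The size cannot be established from the documents. The illustration of about 6 to 35 of 115 patients per arm rests on an assumed 5% to 30% prevalence and on the planned arm sizes. The conclusion about the counting rule depends on neither. The documents do not support any claim that progression is concealed, that emergent ocular events are missed, or that the abbreviated report as listed is affected. The fault matters wherever the SAP 11.6 table is produced.

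**What to change.** In SAP 11.6 and Protocol 7.3.4.5.3, replace or supplement the period count with shift tables by eye and by opacity type (nuclear, cortical, posterior subcapsular):

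- screening grade to worst open-label grade, overall;
- screening grade to worst double-blind grade, by arm.

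Screening is the right main reference because the plan's stated safety baseline is the last assessment before the first open-label dose (Protocol 7.3.4; SAP 11.0). Use the word cataract only for grade 2, in line with Protocol 6.5.2, and call grade 1 lens opacity.

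As a supplementary double-blind table, show the shift from Visit 13 grade to worst double-blind grade by arm, to separate changes that arose before randomization from later ones. Add a note that the Visit 13 eye examination may take place up to 7 days after randomization (Protocol 8.4.4), so this reference can fall after double-blind dosing has begun. That is why it should not be the main table.

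All grades needed are already collected at Visits 1, 13 and 26/ET. The cost is minor programming, revised wording, and one additional reference point to explain.
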